#### **Table 1. Sample ADA Status**

Sample ADA Status	Definition	
Baseline ADA-positive sample	ADA is detected in the last sample before initiation of treatment	
Baseline ADA-negative sample	ADA is not detected in the last sample before initiation of treatment	
ADA-positive sample	1) an ADA detected (positive seroconversion) sample in a subject for whom ADA is not detected at baseline, or (2) an ADA detected sample with ADA titer to be at least 4-fold or greater ( $\geq$ ) than baseline positive titer	
ADA-negative sample	ADA sample that is not deemed ADA-positive	

Next, using the sample ADA status, subject ADA status is defined as follows:

ADA Status	Definition	
Baseline ADA-positive A subject with baseline ADA-positive sample		
ADA-positive	A subject with at least one ADA positive-sample relative to baseline at any time after initiation of treatment	
ADA-negative	A subject with no ADA-positive sample after the initiation of treatment	

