### 5.3.4 Immunogenicity Assessments

Blood samples will be collected before the infusion on Cycles 1, 2, 3, 4, 5, 9, 13, and 21, and at the 28 (±7) days and 100 (±7) days End-of-Treatment Visits to measure ADA for cabiralizumab and nivolumab. ADA for cabiralizumab in serum will be measured by a validated bridging ECLA that utilizes Meso Scale Discovery (MSD) technology. ADA for nivolumab in serum will be measured by a validated ECLA method.

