### 7.2 Study Population

- Enrolled Population: All subjects who signed the ICF and are approved for enrollment with a study subject number assigned by sponsor or designee.
- Response-Evaluable Population based on investigator assessment: Subjects who have a measurable lesion at baseline and one of the following: 1) at least 1 post-baseline tumor assessment, 2) clinical progression, 3) death.
- Response-Evaluable Population based on central review assessment: Subjects who have one of the following: 1) at least 1 post-baseline tumor assessment, 2) clinical progression, 3) death.
- Safety Population: All subjects who receive any dose of cabiralizumab and/or nivolumab. This is the population of primary interest for the summaries of demographics, baseline characteristics, prior therapy, exposure, and safety. Summaries of OS, PFS, and ORR will also be provided for this population.
- PK Concentration Population: All subjects who receive at least one dose of cabiralizumab and/or nivolumab and have at least one available serum concentration data.
- PK Evaluable Population: Subjects in the PK Concentration Population who have adequate PK assessments to reliably derive at least one PK parameter. This is the population of primary interest for the summaries of the PK parameters and exploratory analyses of the association of PK data with efficacy measures.
- Biomarker Subjects: All subjects who receive at least one dose of cabiralizumab and/or nivolumab and have available biomarker data.
- Immunogenicity Subjects: All subjects who receive at least one dose of cabiralizumab and/or nivolumab and have available ADA data.

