## 7.6.8 Immunogenicity

### Summary:

The number (%) of subjects with the following anti-drug responses will be reported for immunogenicity subjects. The on-treatment period starts at first dose and beyond.

- baseline nivolumab ADA-positive
- baseline nivolumab ADA-negative
- baseline cabiralizumab ADA-positive
- baseline cabiralizumab ADA-negative
- nivolumab ADA-positive
- nivolumab ADA-negative
- cabiralizumab ADA-positive
- cabiralizumab ADA-negative

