### **Clinical Implications:**

Effect of immunogenicity on clearance of cabiralizumab and nivolumab will be explored. The summary of trough concentration of cabiralizumab and nivolumab will be summarized respectively by postbaseline cabiralizumab and nivolumab ADA status.

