#### 7.7.2 **PK Parameters**

The PK evaluable population will be used for all summaries of the PK parameters. Summary statistics will be tabulated for each PK parameter by individual or combined cohort with different dose and regimen. Geometric means and coefficients of variation will be presented for Cmax, AUC(0-T), AUC(TAU), Cmin, Ctrough, CL, Vss, MRT and AIs. Medians and ranges (minimum and maximum) will be presented for Tmax. Means and standard deviations will be presented for other PK parameters (i.e., t1/2).

Pharmacokinetic parameters of cabiralizumab will be derived from the serum concentration versus time profiles for the intensively sampled Cycle 1, Day 1 and Cycle 8, Day 1 dose administration in both Phase 1a and Phase 1b of the study. Individual PK parameter values will be derived by non-compartmental methods by a validated PK analysis program using actual times.

Parameter	Units	Definition
Cmax	µg/mL	Maximum observed serum concentration
Tmax	h	Time of maximum observed serum concentration
AUC(0-T)	μg.d/mL	Area under the serum concentration-time curve from time zero to time of last quantifiable concentration
AUC(TAU)	µg.d/mL	Area under the serum concentration-time curve in one dosing interval
Cmin	µg/mL	Minimum observed serum concentration during a dosing interval (excludes pre-dose concentration before the first dose)
Ctrough	µg/mL	Concentration associated with the sample at the end of each dose interval.
CL	L/d	Total body clearance calculated Dose divided by AUC(TAU) for Cycle 8, Day 1
AI_AUC	-	AUC accumulation index; ratio of AUC(TAU) for Cycle 8, Day 1 to AUC(TAU) after the first dose
AI_Cmax	-	Cmax accumulation index; ratio of Cmax from any cycles to Cmax after the first dose
AI_Cmin	-	Cmin accumulation index; ratio of Cmin for Cycle 8, Day 1 to Cmin after the first dose
AI_Ctrough	-	Ctough accumulation index; ratio of Ctrough from any cycles to Ctrough after the first dose
pAUCe	%	Percent of AUC extrapolated from the last quantifiable concentration to infinity (Cycle 1, Day 1 only)
λz	d-1	Slope of terminal log-linear elimination phase
Adj R 	-	Adjusted R  of terminal elimination phase
Lz_Start	d	The time point starting the log-linear elimination phase defining the terminal half-life
Lz_End	d	The time point ending the log-linear elimination phase defining the terminal half-life

Parameter	Units	Definition			
Lz_N	-	Number of time points in the log-linear elimination phase defining the terminal half-life			

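### As the SAP is worded, a dosed subject with no post-baseline ADA sample counts as ADA-negative, so treatment-emergent ADA incidence is understated by the unsampled share

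*SAP*

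**What the plan says.** Immunogenicity is a secondary endpoint in both phases (SAP 4.2). Four parts of the SAP fix how it is counted.

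- **Subject status (SAP 4.2, Table 1.1).** Positive is "A subject with at least one ADA positive-sample relative to baseline at any time after initiation of treatment". Negative is "A subject with no ADA-positive sample after the initiation of treatment".
- **Analysis set (SAP 7.2).** Immunogenicity Subjects are "All subjects who receive at least one dose of cabiralizumab and/or nivolumab and have available ADA data".
- **Denominator (SAP 7.6.8).** "The number (%) of subjects with the following anti-drug responses will be reported for immunogenicity subjects". The same list holds the baseline rows and the post-treatment positive and negative rows, for both drugs.
- **Trough comparison (SAP 7.6.8, Clinical Implications).** "The summary of trough concentration of cabiralizumab and nivolumab will be summarized respectively by postbaseline cabiralizumab and nivolumab ADA status".

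Protocol 5.3.4 sets the sampling: "Blood samples will be collected before the infusion on Cycles 1, 2, 3, 4, 5, 9, 13, and 21", plus the two End-of-Treatment visits at 28 and 100 days. Protocol 7.4.5 describes the ADA frequencies and likewise asks for no post-baseline sample.

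**The concern.** The positive definition needs evidence and the negative one does not. A subject who was never sampled on treatment cannot be positive and satisfies the negative definition automatically. A Cycle 1 pre-dose sample is enough to place that subject in the analysis set. An untested subject is therefore counted as a tested negative.

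The error always runs downward. Its size follows the proportion of each cohort with no post-baseline sample, so cohorts that differ in that proportion become less comparable on a secondary endpoint.

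There is also a gap for subjects with no baseline sample. Table 1 defines a positive sample relative to baseline. If ADA is detected after dosing and the baseline sample is missing, one programmer could call the sample positive, because ADA was not detected at baseline. Another could call it negative, because neither positive criterion is demonstrably met.

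**Working it through.** The documents state no ADA incidence, no missing-sample rate and no ADA-based sample size, so there is no planned figure to reproduce. The check has four steps.

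**1. Does any text add a post-baseline requirement?** None does in Tables 1 and 1.1, SAP 7.2, SAP 7.6.8 or Protocol 7.4.5. The general rule in SAP 7.9.1.1 is no imputation unless specified, but that does not help, because the status definition itself turns absent data into a negative. Elsewhere the SAP does make the distinction. It separates a PK Concentration from a PK Evaluable population (7.2), limits laboratory analyses to safety subjects with data (7.6), and gives thyroid tests a row for missing follow-up values (7.6.7.2).

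**2. Size for incidence.** Let m be the share of Immunogenicity Subjects with no post-baseline ADA sample, and p the positive share among those sampled.

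- Reported incidence = p(1 - m). Incidence among assessed subjects = p. Relative understatement = m; absolute understatement = pm.
- The planned sizes, about 30 per Phase 1b cohort and 210 in Phase 1b, come from SAP 2.1. The values of m and p are assumptions, each taken from 5% to 20%.

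| Set | Assumed m | Assumed p (approx.) | Among assessed | As reported |
|---|---|---|---|---|
| One cohort, 30 | 10% | 10% | 3/27 = 11.1% | 3/30 = 10.0% |
| Phase 1b, 210 | 5% | 10% | 20/200 = 10.0% | 20/210 = 9.5% |
| Phase 1b, 210 | 10% | 10% | 19/189 = 10.1% | 19/210 = 9.0% |
| Phase 1b, 210 | 20% | 20% | 34/168 = 20.2% | 34/210 = 16.2% |

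Over the whole assumed range, pm runs from 0.05 x 0.05 = 0.25 percentage points to 0.20 x 0.20 = 4 percentage points.

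**3. Trough summary.** SAP 7.7.2 defines Ctrough as "Concentration associated with the sample at the end of each dose interval". Protocol Appendix C places pre-infusion PK and ADA draws together at Cycles 2 to 4, 5, 9, 13 and 21. A subject with no post-baseline ADA sample will therefore normally have no trough and drop out of the summary. As an upper bound, suppose every unsampled subject did have a trough and had the same ADA rate as the rest. The truly positive share of the ADA-negative group would be mp / [(1 - m)(1 - p) + m]:

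- m = p = 5%: 0.0025 / 0.9525 = 0.3%
- m = p = 10%: 0.01 / 0.91 = 1.1%
- m = p = 20%: 0.04 / 0.84 = 4.8%

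**4. Monotherapy subjects and nivolumab ADA.** The note to Appendix C says that nivolumab assessments are not done in the Phase 1a monotherapy cohorts. Those subjects still belong to the Immunogenicity Subjects through their cabiralizumab samples, and they literally meet the nivolumab ADA-negative definition. SAP 7.1 presents monotherapy and combination cohorts separately for non-efficacy analyses, so they do not enter the combination denominator.

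**The case against.** The best defence is that the SAP never says outright that unsampled subjects are negative. Subject status is built from sample status, a subject with no on-treatment sample has no on-treatment sample status, and a sensible programmer might leave such a subject unclassified. That is possible, but the written definition does not require it.

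The second defence concerns size, and much of it stands. To have no post-baseline sample, a subject must miss Cycle 2 Day 1 and every later draw, including both End-of-Treatment visits. Protocol 3.1.3 asks all patients to attend those visits whenever treatment stops. Mainly early death, withdrawal of consent or failure to return would leave a subject unsampled, and nothing in the documents supports a share as high as 20%. All analyses are descriptive (Protocol 7), no stated decision rests on ADA incidence, and the listing in SAP 7.6.8 would let a reader recompute the rate. For scale, the exact 95% interval for 3/30 is 2.1% to 26.5%, much wider than the shift to 3/27.

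A reader might infer three stronger claims, and the documents support none of them:

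- *The trough comparison is materially diluted.* The shared draw times make the effect close to nil.
- *Monotherapy subjects dilute the nivolumab rate*, for instance as about 20 of 295 planned subjects (6.8%). Separate presentation prevents this; what remains is a meaningless nivolumab row in the monotherapy columns.
- *Every subject without a baseline sample is unclassifiable.* A subject with post-dose samples and no ADA detected in any of them is negative under Table 1.1. Only a missing baseline together with a detected post-dose sample is ambiguous.

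**Conclusion.** The point holds for incidence. On the literal text, subjects never tested after dosing are counted as ADA-negative, and the reported treatment-emergent rate falls short of the rate among assessed subjects by a relative amount equal to m. With m and p each assumed between 5% and 20%, that is about 0.25 to 4 percentage points. The true m is not given and is probably toward the low end or below. Treating p as the right target assumes that assessed subjects are the group of interest; unsampled subjects, with shorter exposure, might have a different rate.

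The bias is bounded, but its direction is known, it falls on a secondary endpoint, and it comes from a stated rule. It is worth correcting before the tables are produced. It gives no reason to distrust the trough-by-ADA summary, apart from the few subjects who may have troughs but whose ADA group is undefined because the baseline sample is missing.

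**What to change.** In SAP 7.2, define ADA-evaluable subjects separately for cabiralizumab and nivolumab: treated with that drug, with at least one post-baseline ADA result for it. Then:

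- Use this set as the denominator for the ADA-positive and ADA-negative rows in SAP 7.6.8 and for the trough-by-ADA grouping.
- Show other subjects treated with the drug as not assessed, with their number. The nivolumab rows then disappear from the monotherapy columns.
- Keep the wider Immunogenicity Subjects set for baseline prevalence only.
- State in Table 1 how a detected post-dose sample is classified when the baseline sample is missing. Do not require a baseline result for entry to the set, because that would discard subjects who are validly negative as well as on-treatment detections.

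No new data are needed: the cost is a few lines of SAP text and a filter in the programs. The downside is slightly smaller denominators and so slightly less precision. For the example cohort, the exact 95% interval changes from 2.1%-26.5% (3/30) to 2.4%-29.2% (3/27).

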#### **Table 1.1 Subject ADA Status**

#### • Pharmacodynamic Biomarkers

- Changes in whole blood monocyte subsets by flow cytometry
- Changes in cytokine levels by multiplex analysis
- Change in macrophage and T-cell levels in tumor biopsy samples

#### Phase 1b

- **Pharmacokinetic**: The following PK parameters will be derived from concentration-time data for cabiralizumab when appropriate and applicable. Other parameters, such as dose dependency and accumulation ratio, may also be calculated. Accumulation ratio of Cmax and Cmin for nivolumab may be calculated if the data are available.
  - Area under serum concentration-time curve (AUC)
  - $\circ$  Maximum serum concentration (Cmax)
  - $_{\circ}$  Minimum serum concentration (Cmin)
  - Clearance (CL)
  - $_{\odot}$  Volume of distribution at steady state (Vss)

- Accumulation ratio
- $_{\odot}$  Elimination half-life (t1/2)
- **Immunogenicity**: Defined as an immune response to either cabiralizumab or nivolumab, will be assessed by measurement of total anti-cabiralizumab antibodies and total anti nivolumab antibodies from all subjects. Immunogenicity testing will consist of screening, confirmation, and titration for both cabiralizumab and nivolumab. ADA status of a subject will be classified by following the rule in Table 1.
- Pharmacodynamic Biomarkers
  - Changes in whole blood monocyte subsets by flow cytometry
  - Changes in cytokine levels by multiplex analysis
  - Change in macrophage and T-cell levels in tumor biopsy samples

### • Efficacy

- OS will be defined as the time between the first dose of study drug and death.
- DOR will be defined as the time from first confirmed response (CR or PR) until the first objectively documented disease progression per RECIST v1.1 or death due to any cause by investigator assessment
- PFS will be defined for each subject as the time from the first dose to the first objectively documented disease progression per RECIST v1.1 or death due to any cause by investigator assessment.
- ORR per RECIST v1.1 by Central Imaging Review

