### **5.3.2 Efficacy Assessments**

#### **5.3.2.1 Primary Efficacy Parameters**

The primary efficacy parameter is the objective response rate (ORR; number of patients with confirmed response of CR or PR, divided by the total number of patients who are evaluable for a response). Tumor response status will be assessed using RECIST v1.1 by investigator review.

An Independent Radiology Facility will also be established to evaluate imaging data of trial subjects in a central and independent fashion. Board-certified radiologists will determine radiographic response and/or progression following enrollment in according to RECIST v1.1 and/or RANO for Cohort 1b7. Response assessments by independent review will be a secondary endpoint.

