#### 7.5 Efficacy

The best overall response will be calculated following RECIST guideline (version 1.1) by using the best response from visits where tumor assessment is performed. For subjects who discontinue from study, experienced progressive disease, died, or had anticancer therapy, tumor-directed radiotherapy, tumor-directed surgery, the tumor assessment up to the earliest date of the above mentioned events will be included in the best overall response calculation. The best overall response will be calculated respectively for the response assessed by investigator and the central review. Complete or partial response requires confirmation at a subsequent time point at least 4 weeks after the initial response is observed. Establishment of stable disease requires a minimum 42 day duration from first dose of study drug.

For this study, the date of investigator assessed timepoint response will be derived as follows:

- If the timepoint response is CR, PR or SD, the latest scan date, either from target or nontarget lesion will be used as the timepoint response date.
- If the timepoint response is PD, the scan date of earliest sign of progression, either from target or non-target lesion, or new lesion, is used as the timepoint response date.

Efficacy summaries of objective response rate (ORR) and duration of response (DOR) will be provided for the response-evaluable population for investigator assessment as well as central review assessment. The summaries for OS and PFS will be performed for safety population. Response beyond disease progression will not be included in the analysis. If the sample size is too small to do a certain analysis in a group, number and percent of subjects will be provided. For PFS, DOR, and ORR, the main analysis is based on investigator's assessment; the secondary analysis is based on assessment made by central review committee. Additionally, summary of ORR will be performed for the safety population for investigator assessment.

The by prior line of therapies (<=1 and >=2) subgroup analysis will be performed for PFS and OS for pancreatic cancer subjects.

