#### 7.5.2 Secondary Efficacy

Summary:

OS by K-M method. The median survival time along with 95% CI as well as OS rate at 4 months, 6 months, and 12 months will be presented by K-M analysis. OS will also be summarized descriptively (mean, standard deviation, median, first and third quartiles, minimum, maximum). The summary is for safety population.

OS is defined as the time (months) between the first dose of study drug and death due to any cause. Subjects will be censored for this endpoint on the date of the last known date alive if they do not die. The subgroup OS summary will be performed for subjects with pancreatic cancer by prior line of therapies ( $\leq 1$  and  $\geq 2$ ).

- PFS by K-M method for safety population based on investigator assessment
- PFS by K-M method for safety population based on central review assessment
- Subgroup PFS analysis by prior line of therapies (<=1 and >=2) for subjects with pancreatic cancer safety population based on central review assessment.

Sensitivity analysis will be performed for the above PFS analyses by treating clinical PD as event as well. Last dose date + 14 days is considered as event date for clinical PD.

PFS will be defined for each subject as the time (months) from the first dose to the first objectively documented disease progression per RECIST v1.1 or death due to any cause in the absence of documented PD. Censoring for the PFS endpoint is summarized in Table 3. PFS rate at specified timepoints (4 months, 6 months, 12 months) will be presented using K-M method.

- Duration of response (DOR) for responders (confirmed CR or PR) for response-evaluable population based on investigator assessment
- Duration of response (DOR) for responders (confirmed CR or PR) for response-evaluable population based on central review assessment

DOR is defined as the time (months) from date of the first documentation of confirmed response (CR or PR) to the first objectively documentation of progressive disease (PD) or to death due to

any cause in the absence of documented PD. The censoring mechanisms for DOR are similar to those for PFS.

- ORR with corresponding 2-sided 95% CI based on Clopper-Pearson method along with each category of BOR for response-evaluable population based on central review assessment. Time to response will also be included.

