- ORR with corresponding 2-sided 95% CI based on Clopper-Pearson method along with each category of BOR for safety population based on central review assessment. Time to response will also be included.
- The extent of follow-up defined as the time between first dose date and last known date alive (for subjects who are alive) or death date (for subjects who died) will be summarized descriptively for safety population.

Situation	Date of Progression or Censoring	Outcome
No baseline or no evaluable baseline assessment, and no death	Date of first dose	Censored
No post baseline or no evaluable post baseline assessment, and no death	Date of first dose	Censored
No death or disease progression	Date of last evaluable assessment	Censored
Discontinued from study	Date of last evaluable assessment	Censored
New anticancer therapy, tumor- directed radiotherapy, or tumor- directed surgery received without progression reported prior or on the same day	Date of last evaluable tumor assessment prior to the date of initiation of subsequent anticancer therapy	Censored
Disease progression or death	Date of death or first documented progression per RECIST 1.1, whichever is earlier (excludes clinical progression)	Progressed (event)

Table 3: Handling of Missing Assessments and Censoring Rules for PFS

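### Does the option of a RANO read in glioma cohort 1b7 undermine the SAP's central-review results, which all rest on RECIST v1.1?

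*SAP*

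**What the plan says.** Protocol 5.3.2.1, on the independent radiology facility: "Board-certified radiologists will determine radiographic response and/or progression following enrollment in according to RECIST v1.1 and/or RANO for Cohort 1b7". It adds: "Response assessments by independent review will be a secondary endpoint".

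The visible SAP does not mention RANO.

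- SAP 4.2 (Phase 1b efficacy) lists "ORR per RECIST v1.1 by Central Imaging Review".
- SAP 7.5 says "The best overall response will be calculated following RECIST guideline (version 1.1") and then "The best overall response will be calculated respectively for the response assessed by investigator and the central review".
- SAP 7.5.2 plans "PFS by K-M method for safety population based on central review assessment", and central response also with "each category of BOR for safety population based on central review assessment". Its PFS definition and Table 3 count only RECIST progression or death as events. Central duration of response is restricted to confirmed responders, a status that comes from the RECIST best overall response.
- SAP 7.2 defines the central denominator without naming a criterion: "Response-Evaluable Population based on central review assessment: Subjects who have one of the following: 1) at least 1 post-baseline tumor assessment", or clinical progression, or death.

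Other protocol text bears on the question. Section 5.3.2.1.1, directly after the radiology paragraph, has response in measurable disease evaluated by RECIST v1.1, with no carve-out for 1b7. Section 5.3.2.2 ties the additional efficacy parameters to RECIST v1.1. Appendix B note j does the same for response on CT or MRI. Inclusion criterion 1 in section 3.2.2 requires a RECIST-measurable lesion in every cohort, 1b7 included.

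**The concern.** The protocol's and/or, read literally, allows three kinds of central read in 1b7: RECIST only, both, or RANO only. The first two give the SAP what it needs. The third does not. A patient read only by RANO would have no RECIST best overall response, so could not be a central responder, yet might still sit in the denominator because SAP 7.2 asks only for some post-baseline tumor assessment. In PFS, the same patient, if alive, might meet the Table 3 row for lack of an evaluable post-baseline scan and be censored at first dose. Where both reads were made, the RANO results would appear in no visible efficacy summary.

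RANO is not a stray word in this protocol: entry to 1b7 (section 3.2.4.2.7) requires first recurrence documented by RANO. Because SAP 7.1 presents efficacy by cohort, other cohorts would not dilute a distortion in 1b7. At stake are central response rate, duration of response and PFS in that cohort.

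**Working it through.** The documents state no figure on this point, so there is none to reproduce. The check compares the texts and then sizes the worst case.

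**1. Can both documents be followed at once?**

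| Central read in 1b7 | Within Protocol 5.3.2.1? | Supplies SAP 4.2, 7.5, 7.5.2? |
|---|---|---|
| RECIST only | yes | yes |
| RECIST and RANO | yes | yes |
| RANO only | yes, on the literal wording | no |

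Only the rows with a RECIST read satisfy both. The SAP (section 2.4) was written to Amendment 4. On an ordinary reading the protocol lists the permitted criteria and the SAP selects the one it analyses. Protocol 5.3.2.1.1, 5.3.2.2, Appendix B note j and inclusion criterion 1 agree with that selection.

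**2. Does the harm follow under one consistent reading?** The SAP defines neither a tumor assessment in 7.2 nor evaluable in Table 3. Take a living RANO-only patient without clinical progression or new therapy:

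| Reading of both terms | Central response-evaluable denominator | Central PFS |
|---|---|---|
| Any criterion | stays in, no response | censored at last evaluable assessment |
| RECIST only | drops out | censored at first dose |

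Staying in the response-evaluable denominator *and* being censored at first dose requires reading the two terms in opposite ways. In the safety-population response rate the patient stays in the denominator under either reading.

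For a patient who dies, the event need not be dated at death: Table 3 also censors at the last evaluable assessment before new anticancer therapy, so a patient who changed therapy first could be censored.

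**3. Size, if RANO-only reads occurred.** Inputs: about 30 patients in each of 7 Phase 1b cohorts, 210 in all (Protocol 3.2.1); Clopper-Pearson 95% intervals (SAP 7.5). The number of RANO-only patients, k, is not in the documents; 1 to 5 is an assumption.

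- Cohort share: 30/210 = 14.3%.
- Effect per patient with all 30 in the denominator: 1/30 = 3.3 points.
- Highest attainable response rate, (30 − k)/30: k = 1, 96.7%; k = 3, 90.0%; k = 5, 83.3%. These are ceilings, not expected effects.
- Interval for x of n: lower limit is the 2.5% quantile of Beta(x, n − x + 1); upper limit is the 97.5% quantile of Beta(x + 1, n − x).
- One of three assumed responders lost: 3/30 = 10.0% (2.1 to 26.5) becomes 2/30 = 6.7% (0.8 to 22.1).
- Five non-responders kept or dropped: 3/30 = 10.0% against 3/25 = 12.0% (2.5 to 31.2).
- PFS with five patients censored at first dose: 30 − 5 = 25 at risk.

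The shifts of 3.3 and 2.0 points are small beside intervals 24.4 points wide (26.5 − 2.1) and 28.7 points wide (31.2 − 2.5).

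**The case for a change.** The best argument for acting is that the general RECIST statements do not address the central readers of 1b7 specifically, whereas 5.3.2.1 does, and it stops short of guaranteeing a RECIST read. SAP Appendix 1 shows that independent review came in with Amendment 4, so the SAP authors knew of it and still wrote nothing on RANO. If a RANO-only patient turned up, a programmer would have to choose, with data in hand, between non-responder, not evaluable, and some mapping from RANO. One sentence would prevent that.

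Part of this stands. The wording is loose, and the SAP has no rule for such a patient. But the case depends on a read that no passage plans, and an analyst who finds a RECIST read missing has an obvious course: obtain it from the same images, which Protocol 10.1.2 requires sites to keep accessible and archived. That needs no new analysis rule.

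The complaint that RANO reads have no place in the results is weaker still. Text is redacted directly after the central response endpoint in the synopsis and in Protocol 7.3.2.2, and SAP Appendix 1 mentions a Phase 1b exploratory endpoint added alongside independent review. A RANO analysis may lie there, and a supplementary one could duplicate it.

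**Conclusion.** No change is needed. The mismatch between the protocol's optional RANO read and the SAP's RECIST-only central analyses is a looseness of wording that analysts can resolve in only one way if they follow both documents: make the RECIST v1.1 central read in 1b7 and treat any RANO read as additional. Followed that way, the plan gives sound central response, duration of response and PFS results on the same scale as the other cohorts. Tidying the and/or at some later amendment would do no harm, but would change no result that the plan produces.

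The possible effect is limited to secondary, descriptive central-review results in about 30 patients, at 3.3 points of attainable response rate per RANO-only patient. The primary investigator-assessed response rate and overall survival do not depend on it.

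This conclusion assumes that a RECIST read is, or can be, made for each 1b7 patient from the images held. The documents do not show how many patients, if any, were read by RANO alone, and redacted text may say more.
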